## **11 STATISTICS**

#### 11.1 Overview

## **11.1.1 Primary Endpoint**

The primary endpoint of this study is the superiority of HEMOBLASTTM relative to FLOSEAL for the proportion of subjects reaching hemostasis within 3 minutes.

#### **11.1.2** Secondary Efficacy Endpoints

The secondary endpoint of this study is non-inferiority of HEMOBLAST™ relative to FLOSEAL for the proportion of subjects reaching hemostasis within 5 minutes. A margin of 10% (absolute difference) will be used for determining non-inferiority of HEMOBLAST™ relative to FLOSEAL.

## 11.1.3 Safety Outcomes

The rate of occurrence of device malfunctions, device-related AEs, SADEs, and UADEs will be summarized for each treatment group. Events will be summarized by severity.

## 11.1.4 Study Success

Study success will be defined as superiority of HEMOBLASTTM relative to FLOSEAL in the proportion of subjects achieving hemostasis at the 3 minute assessment time point.

## **11.2 General Analysis Considerations**

All statistical analyses will be performed using Power BI, SAS®, and/or R. Unless otherwise specified, all continuous endpoints will be summarized using descriptive statistics, which will include the number of subjects (n), mean, standard deviation, median, minimum, and maximum. All categorical endpoints will be summarized using frequencies and percentages.

## **11.2.1** Analysis Populations

Safety analyses will be performed on the Full Analysis Population, defined as all subjects who were randomized into the study and received study intervention. Efficacy analyses will be conducted on the time to hemostasis (TTH) Analysis Population, defined as all subjects who were randomized, received study intervention, and had a TTH assessment recorded regardless of whether the measurement was censored (defined as the use of an additional hemostatic product or surgical rescue prior to the end of observation time, or failing to achieve and maintain complete hemostasis prior to the end of observation time). Data summaries will be based on the intervention received, regardless of which intervention was randomly assigned.

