## 6.4 Intraoperative Procedures and Evaluations

All subjects will undergo the same intraoperative study evaluations. Intraoperative is defined as the time interval from when the subject enters the surgical suite until the subject exits the surgical suite.

Subjects undergoing the non-emergent cardiothoracic surgeries are eligible for enrollment into the clinical study. The Investigator will perform the surgery per his or her standard procedures, including conventional methods of hemostasis where practical (pressure, ligature, cautery, etc.).

Both test and control devices (not opened or prepared) should be available at the start of each procedure.

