## 6.4.2 Randomization and Hemostat Application

Subjects will be randomized to receive HEMOBLAST™ or FLOSEAL in a 1:1 ratio:

- 52 subjects will be randomized to receive HEMOBLASTTM; and
- 52 subjects will be randomized to receive FLOSEAL.

To ensure balance through time, blocked randomization will be performed. Random block sizes of 2, 4, or 6 will be implemented to conceal treatment allocation. After enrollment and randomization, the assigned hemostat will be used in the subject.

A study-specific stopwatch will be used in the performance evaluations.

After randomization, the assigned hemostat will be opened and prepared. The study-specific stopwatch will be started at the time of hemostat outer packaging opening (time 00:00).

The assigned hemostat will be prepared and applied to the TBS per its respective Instructions for Use (IFU).

At time 03:00 (3 minutes after hemostat packaging opening), hemostasis will be assessed using the SPOT GRADETM. If the TBS is hemostatic (SPOT GRADETM score = 0), the performance evaluations are complete. If the TBS is not hemostatic (SPOT GRADETM score > 0), a re-application of the assigned hemostat will be performed per the respective IFU.

At time 05:00 (5 minutes after hemostat packaging opening), hemostasis will be assessed using the SPOT GRADETM. If the TBS is not hemostatic (SPOT GRADETM score > 0), the Investigator may use any means necessary to obtain hemostasis.

The study-specific stopwatch will run continuously until the 5 minute evaluation time point, except in cases where preparation of the hemostat is interrupted by other activities and obligations of the surgical staff. The study-specific stopwatch will be run by a trained and delegated study staff member. In cases where the individual(s) involved in preparing the hemostat are required to perform other activities, the stopwatch will be paused and restarted when preparation resumes. The number of interruptions will be recorded for each case.

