#### 6.4.5 Intraoperative Data Collection

The following data will be recorded on the Intraoperative CRF:

- Surgical procedure(s)
- Description of TBS
  - Location
  - Conventional means for hemostasis (pressure, suture, cautery, etc.)
- Confirmation of intraoperative eligibility criteria
- Approximate dimensions of target bleeding site
- SPOT GRADETM scores at baseline
  - Assessment of intraoperative eligibility
  - o Immediately prior to hemostatic device application
- SPOT GRADE™ score at 3 minutes
- SPOT GRADETM score at 5 minutes (if hemostasis is not achieved within 3 minutes)
- Randomization
  - Time of randomization
  - o Treatment arm
  - Device lot/batch number data
- Number of incidence(s) of interruption of hemostatic device preparation

- Satisfaction on time and ease of hemostatic device preparation
- Incidence of TBS re-bleeding prior to subject closure
- Incidence of any device deficiencies
- Incidence of any device-related adverse events

Table 7 below shows a timeline of intraoperative procedures.

Time Point (MM:SS)	Study Procedures or Assessments
Prior to 00:00	• Identify Target Bleeding Site (TBS)
	
 
Assign SPOT GRADE™ score
 

	Perform randomization
00:00 (start stopwatch)	
 
Open HEMOBLAST™ or FLOSEAL
 

	packaging and start preparation
0X:XX	• Assign SPOT GRADE ™ score immediately
	prior to hemostat application
03:00	
 
Assign SPOT GRADE™ score
 

	If SPOT GRADE TM score = $0$
	Intraoperative efficacy evaluation completed
	If SPOT GRADE TM score is NOT $0$
	
 
Re-apply HEMOBLASTTM or FLOSEAL
 

05:00	
 
Assign SPOT GRADE™ score
 

	If SPOT GRADE TM score = $0$
	Intraoperative efficacy evaluation completed
	If SPOT GRADE™ score is NOT 0
	Rescue treatment

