## 11.3 Analytic Methods

## 11.3.1 Analysis of Primary and Secondary Efficacy Endpoints

## 11.3.1.1 Analysis Population

Efficacy analyses will be conducted on the TTH Population, defined as all subjects who were randomized, received study intervention, and had a TTH assessment recorded regardless of whether the measurement was censored.

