## 11.3.1.2 Methods of Analysis

The primary efficacy endpoint is the difference in the probability of TTH at 3 minutes comparing HEMOBLASTTM to FLOSEAL. Letting  $\theta$  denote the true difference in the probability of hemostasis at 3 minutes between HEMOBLASTTM to FLOSEAL, the trial will test the null hypothesis H0:  $\theta \le 0$  vs. the alternative hypothesis HA:  $\theta > 0$  using a one-sided level 0.025 Wald test. The resulting p-value based upon the asymptotic normal distribution and a corresponding (2-sided) 95% confidence interval for the difference in binomial proportions (HEMOBLASTTM minus FLOSEAL) will also be computed and reported.

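### The plan's only rule on assigned versus received device, read naturally, puts the 3-minute superiority test and the 5-minute non-inferiority analysis on an as-received basis; efficacy should be by randomised arm (minor)

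*Combined protocol and SAP*

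**What the plan says.** Section 11.2.1 defines a safety population and an efficacy (TTH) population, and then closes with the sentence "Data summaries will be based on the intervention received, regardless of which intervention was randomly assigned". No other sentence in the combined protocol and SAP chooses between assigned and received device.

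The sections on the tests are silent on grouping:

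- Section 11.3.1.1: "Efficacy analyses will be conducted on the TTH Population, defined as all subjects who were randomized", plus receipt of study intervention and a recorded assessment. This says who is included, not in which group they count.
- Section 11.3.1.2: the 3-minute difference, HEMOBLAST minus FLOSEAL, is tested "using a one-sided level 0.025 Wald test".
- Section 11.1.2, for the 5-minute endpoint: "A margin of 10% (absolute difference) will be used for determining non-inferiority". It gives no grouping rule.
- Section 11.1.4: "Study success will be defined as superiority of" HEMOBLAST over FLOSEAL at 3 minutes. The whole success claim therefore rests on the one test.

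On conduct, section 6.4.2 says "After enrollment and randomization, the assigned hemostat will be used in the subject", and section 6.4 says "Both test and control devices (not opened or prepared) should be available at the start of each procedure". Section 6.4.5 lists "Treatment arm" among the randomisation items on the Intraoperative CRF.

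**The concern.** Randomisation makes the two groups comparable only if subjects are compared as they were allocated. Suppose a subject's target bleeding site is treated with the non-assigned device for a reason linked to how easily the site will stop bleeding. An as-received comparison then moves that subject's prognosis into the other group. The trial describes no blinding, and both devices are available at every procedure.

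At stake is the single test that defines study success. A single subject can matter near the boundary, as the hypothetical counts in the working show. The 5-minute non-inferiority analysis has the same gap. There neither grouping is clearly conservative, because crossovers analysed as randomised pull the arms together and can favour a non-inferiority conclusion.

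**Working it through.** **1. The plan's own figure.** Section 11.3.3 uses 0.40 versus 0.10 at 3 minutes, one-sided alpha 0.025 and 90% power. The pooled two-proportion formula gives

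n = [1.96·√(2·0.25·0.75) + 1.2816·√(0.24 + 0.09)]² / 0.30² ≈ 41.7, so 42 per arm.

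The continuity correction (n/4)·[1 + √(1 + 4/(0.30·n))]² raises this to just over 48, so 49 per arm and 98 in total, as stated. Then 98/0.95 = 103.2, rounded up to 104. The sample size is not in dispute and does not depend on the grouping rule.

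**2. One subject near the boundary (hypothetical counts).** Unpooled Wald: z = (p₁ − p₂)/√[p₁(1−p₁)/n₁ + p₂(1−p₂)/n₂].

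- As randomised, 12/52 v 5/52: difference 0.135, z = 1.89, one-sided p = 0.030. The test fails.
- If one FLOSEAL-assigned success had received HEMOBLAST, as received, 13/53 v 4/51: difference 0.167, z = 2.38, p = 0.009. The test passes.

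**3. Error of the as-received test when there is no true effect.** The documents give no switch rate, so these inputs are assumptions: 3-minute rate 0.25 in both randomised arms (midpoint of 0.40 and 0.10), 52 per arm, k switches all in one direction, and success probability s at the switched sites. The values of s are borrowed from the section 11.3.3 device rates to stand for better (0.40) or worse (0.10) prognosis. The non-switchers in the switching arm have rate (13 − k·s)/(52 − k), which keeps that arm's mean at 0.25. Rejection (z > 1.96) was summed exactly over all outcome tables.

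| s | Direction | k = 0 | k = 1 | k = 2 | k = 4 |
|---|---|---|---|---|---|
| 0.40 | FLOSEAL to HEMOBLAST | 2.7% | 3.2% | 4.0% | 5.4% |
| 0.40 | HEMOBLAST to FLOSEAL | 2.7% | 2.2% | 2.0% | 1.4% |
| 0.10 | FLOSEAL to HEMOBLAST | 2.7% | 2.3% | 2.2% | 1.6% |
| 0.10 | HEMOBLAST to FLOSEAL | 2.7% | 3.0% | 3.8% | 4.8% |

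The expected shift for FLOSEAL-to-HEMOBLAST switches is (13 + k·s)/(52 + k) − (13 − k·s)/(52 − k). At s = 0.40 this is 0.58, 1.16 and 2.32 percentage points for k = 1, 2 and 4. Switches unrelated to prognosis (s = 0.25) give no shift and an error of 2.6% to 3.1%. Analysed as randomised, the error in all the prognosis-linked cases is 2.70% to 2.73%.

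**4. Power cost of analysing as randomised.** With rates 0.40 v 0.10, c switches in each direction and switched sites taking the rate of the device received:

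| Evaluable per arm | c = 0 | c = 1 | c = 2 | c = 3 | c = 4 |
|---|---|---|---|---|---|
| 52 (no attrition) | 96.2% | 94.8% | 93.0% | 90.8% | 88.1% |
| 49 (section 11.3.3 evaluable number) | 95.5% | 93.8% | 91.7% | 89.1% | 85.9% |

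Power falls below 90% at 4 each way (8 of 104) with 52 per arm, and at 3 each way (6 of 98) with 49.

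No 5-minute rates are documented, so no figure can be given for the non-inferiority analysis.

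**The case against.** The strongest reply is that the consequence depends on an event the protocol forbids and does not expect. The assigned device must be used. Both devices start unopened, and packaging is opened only after randomisation. Each subject has one target bleeding site. Use of an additional hemostatic product before the assessment counts as failure (11.2.1, 11.2.2). Deviations are recorded (11.2.7) and, outside emergencies, need prior Sponsor approval (15.5). Only full substitution at the target site remains, and without it the two groupings are identical. All of this stands, and it is why the point is minor. It does not supply an analysis rule for the departures that the section 11.2.1 sentence itself contemplates.

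The illustration is also driven by assumptions. Half of the prognosis-linked scenarios lower the error. The 2.7% baseline already exceeds 2.5% because of the Wald test, not the grouping. The one-switch increases (3.0% and 3.2%) are hard to tell from the discreteness of the test, since four prognosis-free switches can give 3.1%. That stands too.

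A reader might go further in either of two ways. One is to say that the plan has no grouping rule at all, so the choice stays open until the data are known. That overstates the ambiguity: the sentence sits under general considerations, directly after the efficacy population, and its ordinary reading covers the efficacy results. The references to an arm in 6.4.5, 11.2.2 and 11.2.5 are a data item, undefined wording and a head count, not a rule for a test. The other is to say that the trial's error rate is inflated in favour of HEMOBLAST. The documents do not support that either, because they report no switches and the direction could be either way.

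**Conclusion.** The point holds as a minor one. Read naturally, the plan runs its sole success test and its non-inferiority analysis by device received and names no as-randomised efficacy analysis. This is the weaker choice for a randomised superiority claim, and the better one is available at almost no cost.

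The practical effect is probably small and is nil if nobody receives the non-assigned device. A clear rise in error needs about two to four substitutions, all in one direction and linked to prognosis; under the stated assumptions it then reaches 3.8% to 5.4%, against about 2.7% as randomised. Those figures rest on an invented switch count and invented prognosis rates. They show what could happen and are not an estimate for this trial.

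**What to change.** 1. State in 11.2.1 and 11.3.1 that the primary and secondary efficacy analyses group subjects by randomised arm within the TTH population, with the as-received grouping as a sensitivity analysis. For the 5-minute non-inferiority analysis, show both groupings side by side.
2. Limit the as-received sentence in 11.2.1 to safety.
3. Optionally, list use of the non-assigned device at the target bleeding site as an important deviation in 11.2.7.

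The cost is a sentence in each of two sections and one sensitivity analysis, plus a bullet if item 3 is adopted. The randomised arm is already on the Intraoperative CRF, so no new data, subjects or procedures are needed. The trade-off is dilution if crossovers occur: two in each direction would take power from 96.2% to 93.0% at 52 per arm, or from 95.5% to 91.7% at 49.

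This restores only part of the protection of randomisation. Subjects who are randomised but not treated would still be left out of the analysis (section 10) and replaced (section 9.1), which is a separate matter.

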## 11.2.3 Subgroup Analyses

Analyses of performance (primary and secondary endpoints) will be presented by baseline bleeding severity. Additionally, the primary and secondary endpoints will be presented stratified by preoperative anticoagulation regimen.

## **11.2.4 Data Transformations**

No transformations of data are planned.

## **11.2.5** Subject Disposition and Characteristics

The number of subjects randomized to each treatment arm will be tabulated. Demographic variables will include age, sex, race, ethnicity, height, weight, and Body Mass Index (BMI). Baseline disease characteristics will include indication(s) for surgery and related co-morbidities/concomitant illnesses. All continuous endpoints will be summarized using descriptive statistics, that will include the number of subjects (n), mean, standard deviation, median, minimum, and maximum. All categorical endpoints will be summarized using frequencies and percentages.

## **11.2.6 Subject Compliance**

Because the study device will be applied by the investigator during a single surgery, subject compliance with completing the study evaluations is not an issue and will not be reported.

## **11.2.7** Protocol Deviations

Eligibility criteria that were not met will be listed along with whether or not an exception was granted. Important protocol deviations will be summarized by treatment group. Important protocol deviations are defined as:

- Any unauthorized protocol deviations that result in a significant added risk to the study subject;
- Performing study-specific activities without subject written informed consent;
- Non-adherence to eligibility criteria without prior Sponsor approval; and
- Non-adherence to Good Clinical Practice and/or applicable regulations;
- Protocol deviations will be summarized in tables produced by the Medical Monitor or Clinical Research Associate.

Protocol deviations will be either self-reported by the study site or identified by the Sponsor/Sponsor representative during site visits. Protocol deviations will be recorded and retained in the study files.

## 11.3 Analytic Methods

## 11.3.1 Analysis of Primary and Secondary Efficacy Endpoints

## 11.3.1.1 Analysis Population

Efficacy analyses will be conducted on the TTH Population, defined as all subjects who were randomized, received study intervention, and had a TTH assessment recorded regardless of whether the measurement was censored.

## 11.3.1.2 Methods of Analysis

The primary efficacy endpoint is the difference in the probability of TTH at 3 minutes comparing HEMOBLASTTM to FLOSEAL. Letting  $\theta$  denote the true difference in the probability of hemostasis at 3 minutes between HEMOBLASTTM to FLOSEAL, the trial will test the null hypothesis H0:  $\theta \le 0$  vs. the alternative hypothesis HA:  $\theta > 0$  using a one-sided level 0.025 Wald test. The resulting p-value based upon the asymptotic normal distribution and a corresponding (2-sided) 95% confidence interval for the difference in binomial proportions (HEMOBLASTTM minus FLOSEAL) will also be computed and reported.

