# **3 DEVICE DESCRIPTION**

## 3.1 Test Device Description and Indication for Use

HEMOBLAST™ consists of a powder composed of collagen, chondroitin sulfate, and thrombin. The powder is dry, sterilized, biocompatible, and non-pyrogenic. It is resorbed within 4 weeks. No preparation, mixing or heating is required.

HEMOBLAST™ is composed predominantly of highly purified porcine collagen with smaller amounts of bovine chondroitin sulfate and human pooled plasma derived thrombin. Each device contains a maximum of 1500 IU of thrombin. Plasma donations are from US plasma centers only. All individual donations of the plasma were tested for HBsAg, anti-HIV1/-HIV2, and anti-HCV and found to be negative. The plasma pools were tested and found to be non-reactive for HCV RNA, HBV DNA, and HIV1 RNA as determined by PCR (NAT). The product complies with the specifications of the manufacturer and World Health Organization (WHO).

The manufacturing procedures for HEMOBLAST™ include processing steps designed to reduce the risk of viral transmission.

HEMOBLASTTM is approved by the United States Food and Drug Administration (FDA) for use in surgical procedures as an adjunct to hemostasis when control of minimal, mild, and moderate bleeding by conventional procedures is ineffective or impractical, except in neurosurgical, ophthalmic, and urological procedures.

The Instructions for Use are included as Appendix A.

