## 6.4.1 Intraoperative Inclusion Criteria

A subject must then meet all of the following intraoperative inclusion criteria:

- Subject does not have an active or suspected infection at the surgical site;
- Subject in whom the Investigator is able to identify a TBS for which any applicable conventional means for hemostasis are ineffective or impractical; and
- Subject has a TBS with minimal, mild, or moderate bleeding.1

If all of these intraoperative eligibility criteria are met, then the subject is formally enrolled into the clinical study and randomized. Each subject will have one TBS assessed and documented for the purposes of this study.

The bleeding severity of the TBS will be assessed via the SBSS/SPOT GRADETM for intraoperative inclusion, which is immediately prior to enrollment. The bleeding severity of the TBS will also be assessed and confirmed immediately prior to hemostat application, as bleeding severity may change between the time of enrollment and when the hemostat is ready to be applied. Both bleeding severities will be recorded on the Intraoperative CRF. Both bleeding severities will be presented in the analysis of the study data.

If the bleeding severity at the time when the hemostat is ready to be applied is not minimal, mild, or moderate bleeding, then the TBS will not be treated. If another suitable TBS is identified, the subject may undergo intraoperative evaluations for that TBS. If another suitable TBS is not identified, the subject will be withdrawn from the clinical study.

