## 6.4.3 Bleeding Severity and Hemostasis Evaluations

Bleeding severity and hemostasis will be assessed using the SBSS / SPOT GRADE™ at each time point.

A SPOT GRADETM score of 0 is equivalent to hemostasis. All other SPOT GRADETM scores are considered failure of hemostasis. See below in Table 6.

SBSS Score	0	1	2	3	4	5
Verbal Descriptor	None	Minimal	Mild	Moderate	Severe; not immediately life- threatening	Extreme; immediately life- threatening
Visual Descriptor	Dry	Oozing	Pooling	Flowing	Streaming	Gushing
Expected Intervention(s)	None	Manual pressure, cautery, adjuvant hemostat(s)	Manual pressure, cautery, suture, adjuvant hemostat(s)	Manual pressure, cautery, suture, adjuvant hemostat(s)	Manual pressure, cautery, suture, staples, tissue repair	Manual pressure, cautery, suture, staples, tissue repair
Maximum Expected ACS-ATLS Shock Risk Class	1	1	1	2	3	4
Hemostasis	Yes	No	No	No	No	No

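### Cheap improvement, not an error: the 3-minute primary comparison could be stratified by the pre-randomisation SPOT GRADE that is already collected

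*Combined protocol and SAP*

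**What the plan says.** Section 11.3.1.2 sets a one-sided 0.025 Wald test of the difference in the probability of hemostasis at 3 minutes, with a two-sided 95% "confidence interval for the difference in binomial proportions". It names no covariate. Section 6.4.2 describes 1:1 blocked randomisation and no stratification by severity.

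The outcome is read on the SPOT GRADE: in 6.4.3, a "score of 0 is equivalent to hemostasis". The same scale is scored twice before treatment. Section 6.4.1 takes one score "for intraoperative inclusion, which is immediately prior to enrollment", and Table 7 (in 6.4.5) places it before randomisation. The other is taken "Immediately prior to hemostatic device application" (6.4.5). By then the arm is known, since 6.4.2 says: "After randomization, the assigned hemostat will be opened and prepared". Section 6.4.5 lists both scores under baseline.

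Sections 5.4 and 11.2.3 present results by baseline bleeding severity. Section 6.4.1 adds "Both bleeding severities will be presented in the analysis of the study data". No section says which score defines the subgroups. Section 6.4.1 also lets the site change after randomisation: "If another suitable TBS is identified, the subject may undergo intraoperative evaluations for that TBS".

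For 5 minutes, 11.1.2 gives an absolute margin of 10%. Section 11.3.1.2 writes no test for it.

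**The concern.** A baseline measurement of the outcome scale is often the best single covariate a trial has. Here it is on the Intraoperative CRF for every enrolled subject and the primary comparison does not use it. Because randomisation is not stratified by severity, balance on it is left to chance. If grade predicts hemostasis, stratifying by it recovers some precision without new data.

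The two scores also differ in kind. The eligibility score precedes assignment. The pre-application score follows assignment, pack opening and a preparation interval that may differ by device, since 3.1 says of HEMOBLAST: "No preparation, mixing or heating is required". Subgroups built on the second score would condition on a post-assignment value. Leaving baseline undefined leaves that choice open until the data are in hand.

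**Working it through.** **The plan's own figure.** Inputs from 11.3.3: 40% v 10%, one-sided alpha 0.025, power 90%.
- Pooled-variance formula: n = [1.960 x sqrt(2 x 0.25 x 0.75) + 1.282 x sqrt(0.40 x 0.60 + 0.10 x 0.90)]^2 / 0.30^2 = (1.200 + 0.736)^2 / 0.09 = 41.7.
- Continuity correction: (41.7/4) x [1 + sqrt(1 + 4/(41.7 x 0.30))]^2 = 48.1, so 49 per arm, as stated.
- Attrition: 98 / 0.95 = 103.2, so 104, as stated.

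**Power of the planned crude test.** The unpooled standard error is sqrt(0.33/n).
- 49 per arm: 0.30/0.0821 - 1.960 = 1.70, power 95.5%.
- 52 per arm: 0.30/0.0797 - 1.960 = 1.81, power 96.5%. Simulation gives about 96.2%.

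**What stratifying can gain.** The documents give neither the grade mix nor the link between grade and outcome, so both are assumed. For large samples, the variance of a grade-adjusted risk difference relative to the crude one is

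{sum of share x [p1(1-p1) + p0(1-p0)] + half the sum of share x (d - 0.30)^2} / 0.33,

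where p1, p0 and d are the two rates and their difference within a grade.

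Example: mix 40/40/20, odds ratio 4 per grade in both arms, overall rates held at 40% and 10%. HEMOBLAST rates are then 0.641, 0.309, 0.100 and FLOSEAL rates 0.188, 0.055, 0.014. The first sum is 0.195 + 0.085 = 0.280. Half the second is 0.0097. The ratio is 0.290/0.33 = 0.88, a fall of about 12% before the small-sample cost of stratifying.

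**With that cost included.** Simulation, 60,000 trials per scenario, 52 per arm: crude Wald against the Mantel-Haenszel risk difference with Sato variance.

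| Odds ratio per grade, both arms | Variance change | Power crude | Power stratified | Verdicts differ |
|---|---|---|---|---|
| 1 (not prognostic) | +2.2% | 96.2% | 96.0% | 0.9% |
| 1.5 | +0.6% | 96.2% | 96.3% | 1.1% |
| 2 | -1.9% | 96.2% | 96.6% | 1.5% |
| 3 | -6.6% | 96.1% | 97.2% | 2.0% |
| 4 | -10.1% | 96.3% | 97.8% | 2.3% |

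- The mean 95% half-width is 15.4 points crude, and 15.6 (odds ratio 1) to 14.9 (odds ratio 4) stratified.
- If grade is prognostic in one arm only (odds ratio 4), the variance change is about -4% (HEMOBLAST only) or +1% (FLOSEAL only).
- If the true rates were 30% v 10%, power would be about 75% crude and 74.7% to 79.5% stratified.
- One-sided type I error at equal rates of 10%, 25% and 40% is 2.7% to 3.1% crude and 2.6% to 2.8% stratified.
- If 10% or 20% of subjects are treated at a second site with an unrelated grade, the -10.1% shrinks to -7.4% or -5.6%.

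**Adding more factors.** When nothing is prognostic, the variance cost is about 2.1% for grade alone, 4.9% for grade by a two-level anticoagulation factor, and 16.4% for grade by five equal sites.

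**5 minutes.** Assume equal true rates of 70%, one-sided 0.025 and 52 per arm. The standard error is sqrt(2 x 0.70 x 0.30/52) = 0.0899, and 0.10/0.0899 - 1.960 = -0.85, so crude power is about 20% (21% by simulation). Stratified power is about 20% to 24%. At the edge of the margin with high rates (95% FLOSEAL, 85% HEMOBLAST), one-sided error is about 3.8% to 4.0% stratified against 3.4% to 3.6% crude.

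**Subgroups.** With about 21 subjects per arm in a grade (40% of 52) and a 25% rate, the 95% half-width is 1.96 x sqrt(2 x 0.25 x 0.75/21) = 26 points.

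**The case against.** The best case for leaving the plan alone is that nothing is broken. The crude test is valid under randomisation, its sample size reproduces, and its power already exceeds the target. At the design rates, stratifying moves power by -0.2 to +1.5 points and changes the verdict in about 1% to 2% of trials. The documents do not show that grade predicts hemostasis; if it does not, the primary analysis becomes slightly worse. Severity is not ignored either, because results are already to be shown by grade and both scores presented. All of this stands. It limits the point to an option, but does not remove it: the cost is bounded at about 2% in variance and the possible gain is larger.

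A reader might infer that the primary analysis is wrong or short of power. The calculation above shows neither. A reader might also infer that stratifying improves a planned crude 5-minute test. The documents give a margin but no 5-minute test, so there is no stated method to improve. Stratifying leaves power low at the assumed rates, and at high rates its error control is slightly worse.

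The case of a second bleeding site is a fair objection. The pre-randomisation score then describes a site that was not treated, which weakens the reason for using it in those subjects.

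**Conclusion.** This is worth considering as a low-cost improvement to the 3-minute analysis. Its size is a variance change between about +2% and -10%, with power of 96.2% crude against 96.0% to 97.8% stratified. That range rests on an assumed 40/40/20 mix, odds ratios of 1 to 4 per grade in both arms, and the plan's own 40% v 10%. Prognosis in one arm only leaves about -4% or +1%.

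The undefined baseline score is a clarification only. It might be read as a threat to the trial's conclusion, but 5.4 calls the by-severity results exploratory, 11.1.4 rests success on the overall 3-minute comparison, and the subgroup intervals are wide in any case.

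**What to change.** Make these changes before data are analysed.

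1. **11.3.1.2, 3 minutes.** Name as the deciding analysis the Mantel-Haenszel risk difference with Sato variance, stratified by eligibility SPOT GRADE (minimal, mild, moderate), at one-sided 0.025. Report the crude difference beside it. This keeps the risk-difference scale of the current text. Use grade alone; anticoagulation stays a subgroup under 11.2.3.
2. **Pooling rule, based on grade counts by arm only.** If a grade has no subjects in one arm, pool minimal with mild, moderate with mild, or mild with moderate. At 40/40/20 this is needed in under 0.01% of trials; if one grade holds 5% of subjects, in about 13%.
3. **Second bleeding site.** Use the first site's pre-randomisation score as the stratum. Report the number of such subjects by arm and show the treated site's grade descriptively.
4. **5 minutes.** Write the method out. The same stratified risk difference may be used, with the lower 95% limit required to exceed -10%. If rates near 85% to 95% are expected, consider a score-type interval, and make that choice in advance.
5. **5.4 and 11.2.3.** Define baseline bleeding severity as the eligibility score taken before randomisation and say which bleeding site it refers to. Tabulate the pre-application score by arm as descriptive, which still meets 6.4.1.

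Cost: a few sentences, with no change to sample size or treatment. Both scores are already on the CRF, but the first site's score must be kept when a subject moves to a second site. The downsides are about 2% more variance if grade is not prognostic, and a stratum label that does not describe the treated site in second-site subjects.
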